6.4 Early Termination Visit

Participants who leave the study before week 48 (the final scheduled visit to the NIH), voluntarily or otherwise, will be urged to return to the NIH CC for an early termination visit. As with the follow-up visits, participants will have a physical exam, have their medical and medication history reviewed, be assessed for AEs, and have blood drawn for clinical and research evaluations. If a participant decides to leave the study between weeks 48 and 96, then the telephone call follow-up will be conducted at that time, with the participant's agreement.

7 Research Procedures/Evaluations

Medical history and physical exam.

Blood draw: The amount of blood drawn for research purposes will be within the limits allowed for adult research participants by the NIH CC (Medical Administrative Policy

95-9, Guidelines for Limits of Blood Drawn for Research Purposes in the Clinical Center: <http://cc-internal.cc.nih.gov/policies/PDF/M95-9.pdf>).

Safety labs at each visit will include CBC/diff, chemistry panels (acute, hepatic, and mineral), lipid panel, TSH and T4, ACTH, cortisol, plasma HIV viral load, and immune profile including CD4 count.

Research evaluations on blood and/or leukapheresis will include the following:

- Fluorescence-activated cell sorting analysis, including CD4+ and CD8+ populations and subsets, and PD-1 expression on CD4+ and CD8+ T cells.
- Assays to measure CD8+ T-cell anti-HIV activity.

Other research evaluations may include but are not limited to the following:

- Frequency of CD4+ T cells carrying HIV pro-viral DNA and cell-associated HIV RNA.
- Frequency of HIV-specific CD4+ and CD8+ T cells.
- T-cell activation and soluble markers of inflammation.
- Gene expression profiling of T cells.
- Antibodies to HIV-specific and other proteins using the luciferase immunoprecipitation system assay.
- Cell-associated p24 antigen levels (to be performed at Merck).
- Plasma levels of pembrolizumab (to be performed at Merck).

Leukapheresis: Leukapheresis will be performed by trained members of the Apheresis Unit under supervision of the medical staff of the Department of Transfusion Medicine at the NIH CC according to CC standard operating procedures. If leukapheresis cannot be performed for technical reasons (eg, poor venous access) or due to scheduling or logistical issues, then 80 mL of blood will be drawn instead. Samples collected from this procedure will be used for assays to measure CD8+ T-cell anti-HIV activity and may be utilized for research evaluations as summarized above.

8 Potential Risks and Benefits

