4.4 Justification for Exclusion of Special Populations

Females who are pregnant or of reproductive potential: Dedicated developmental and fetal toxicity studies of pembrolizumab have not been conducted in humans or animals. However, animal models of the PD-1/PD-L1 pathway suggest that perturbations may affect the maternal immune response to fetal tissue. Human IgG4 antibodies (the IgG subtype of pembrolizumab) are also known to cross the placental barrier and be transmitted from mother to fetus. Additionally, pregnancy may affect the participant's immune response. Therefore, pregnant participants are excluded from this study. Per recommendations in the pembrolizumab package insert, contraception (for this study, two forms, one of which must be a barrier-based method, see Section 4.2) will be required from 30 days prior through 120 days after the pembrolizumab dose.

Breastfeeding: It is unknown whether pembrolizumab is excreted in human milk. Since many drugs are excreted in human milk, and because of the potential for serious adverse reactions (ARs) in the nursing infant, participants who are breast-feeding are not eligible for enrollment.

Exclusion of children: Because there are insufficient data regarding dosing or AEs available in adults to judge the potential risk in children, and because this is the first safety study in HIV-infected patients without cancer, children are excluded from this study.

5 Study Agent/Interventions

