6.3 Follow-up (weeks 1-96)

Participants will return for follow-up visits at weeks 1, 2, 3, 4, 6, 9, 12, 16, 24, 36, and 48. All visits through week 6 will have a window of ± 4 days; visits from week 9 onward will have a window of ± 7 days. At all visits, participants will have the following:

- Review of medical and medication history.
- Targeted physical exam, including weight, vital signs, and a symptom-directed evaluation.
- Assessment of AEs.
- For participants of reproductive potential, counseling concerning the importance of consistently using two forms of effective birth control in light of the potential risk of pembrolizumab to a developing fetus.
- Blood draw for clinical and research evaluations (see [Section 7](#)).
- Pregnancy test (serum or urine, for participants of childbearing potential only).
- Optional follow-up leukapheresis at weeks 3 or 4 and 12. Refusal to undergo leukapheresis will not otherwise affect participation in the study.

Follow-up telephone calls at weeks 60, 72, 84, and 96 (± 2 weeks) will be conducted to see if any AEs potentially related to pembrolizumab occurred during the prior 12 weeks. Participation in this study will end after the week 96 call.

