12.3.2.4 Pregnancy

Participants who inadvertently impregnate a partner after receiving study agent will be instructed to immediately inform the investigator. All pregnancies occurring within 120 days of pembrolizumab administration will be reported on the Pregnancy Notification/Outcome Form to the CSO within 1 business day from site awareness.

The investigator will make every effort to obtain pregnancy outcome data (e.g., delivery outcome, spontaneous or elective termination of the pregnancy). SAEs and the outcome of the pregnancy will be reported to the CSO within 3 business days of the site's awareness.

Although pregnancy itself is not an AE, events that meet SAE criteria during pregnancy, delivery, or in the neonate (eg, miscarriage, congenital anomaly/birth defect) are reportable on the SERF.

In the event of pregnancy, the following steps will be taken:

- Report to the CSO, IRB, and DSMB.
- Unblind participant.
- If participant received pembrolizumab, advise research participant that his partner should notify her obstetrician of study participation and study agent exposure.
- Maintain regular (e.g., monthly) contact with the participant to track the progress and outcome of the pregnancy, including any untoward events, AEs, and SAEs.

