Appendix B: Schedule of Procedures and Evaluations

Evaluation	Study week (day window)														Early termination visit
	Screening ^a Week -6 to 0	Baseline Day 0	1 (± 4)	2 (± 4)	3 (± 4)	4 (± 4)	6 (± 4)	9 (± 7)	12 (± 7)	16 (± 7)	24 (± 7)	36 (± 7)	48 (± 7)	60, 72, 84, 96 (all ± 14)	
Informed consent	X														
Physical exam with vital signs	X		X	X	X	X	X	X	X	X	X	X	X		X ^b
Medical history/medication review	X		X	X	X	X	X	X	X	X	X	X	X	X ^c	X ^d
Counseling on use of birth control	X	X	X	X	X	X	X	X	X	X	X	X	X	X	X ^c
Blood draw for screening labs	X														
Urinalysis	X														
Urine Pregnancy t(for participants of childbearing potential only)	X	X	X	X	X	X	X	X	X	X	X	X	X		
ECG	X														
HLA typing	X														
Blood draw for storage	X														
Leukapheresis	X ^e				X ^{f,g}	X ^{f,g}			X ^f						

Evaluation	Study week (day window)														Early termination visit
	Screening ^a Week -6 to 0	Baseline Day 0	1 (± 4)	2 (± 4)	3 (± 4)	4 (± 4)	6 (± 4)	9 (± 7)	12 (± 7)	16 (± 7)	24 (± 7)	36 (± 7)	48 (± 7)	60, 72, 84, 96 (all ± 14)	

Administration of pembrolizumab ^h or placebo		X														
AE assessment			X	X	X	X	X	X	X	X	X	X	X	X	X ^c	X ^d
Blood draw for clinical/research labs, storage		X	X	X	X	X	X	X	X	X	X	X	X			X ^b

AE = adverse event; ECG = electrocardiogram; X = to be performed.

- a Screening can be scheduled over multiple visits per convenience of the participant and study team.
- b This assessment will only be conducted if the early termination visit is on or before week 48.
- c This assessment will be conducted over the phone.
- d This assessment will be conducted over the phone if the early termination visit is after week 48.
- e Will be performed after confirmation of eligibility. If the participant cannot do this procedure (eg, poor venous access), then an extra 80 mL of blood will be collected for storage and research.
- f This procedure is optional. If the participant declines to do it or cannot (eg, poor venous access), then an extra 80 mL of blood will be collected for storage and research.
- g Leukapheresis will be done at either week 3 or 4, not both. Scheduling will depend on the convenience of the participant and study team.
- h 200 mg via intravenous infusion for 30 minutes.

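### No pregnancy test is listed at early termination, even within 120 days of dosing, and the instruction to report a pregnancy at once reaches only participants who impregnate a partner

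*Combined protocol and SAP*

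**What the plan says.** Inclusion criterion 14 in Section 4.2 covers both becoming pregnant and impregnating a partner, so participants of childbearing potential are eligible. Section 4.4 says that contraception "will be required from 30 days prior through 120 days after the pembrolizumab dose". It gives the reasons: IgG4 antibodies cross the placenta, PD-1 pathway perturbation may affect the maternal immune response to fetal tissue, and no dedicated fetal toxicity studies have been done.

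Section 6.3 lists procedures for every follow-up clinic visit to week 48. One item, separate from the clinical and research blood draw, is "Pregnancy test (serum or urine, for participants of childbearing potential only".

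Under Section 6.4, participants who leave before week 48 "will be urged to return to the NIH CC for an early termination visit". After a comparison with the follow-up visits, the section gives the content: "participants will have a physical exam, have their medical and medication history reviewed, be assessed for AEs, and have blood drawn". In Appendix B, the early termination column marks the exam, history, birth-control counseling, AE assessment and blood draw, but not the pregnancy test.

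Section 12.3.2.4 opens with the instruction to participants: "Participants who inadvertently impregnate a partner after receiving study agent will be instructed to immediately inform the investigator". The site's own duty is wider: "All pregnancies occurring within 120 days of pembrolizumab administration will be reported".

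**The concern.** The protocol treats fetal exposure as a risk that justifies a test at every scheduled clinic visit. The early termination visit is the last planned in-person contact for someone who leaves, and it is the one post-dose clinic visit with no test. No reason is given.

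The actions in Section 12.3.2.4 are to notify the Clinical Safety Office within one business day, inform the IRB and DSMB, unblind, and follow the pregnancy to outcome. All of them depend on the site knowing. For an enrolled woman, scheduled testing is the protocol's explicit means of finding out. When she leaves early that testing stops, and no written instruction to report her own pregnancy replaces it. A pregnancy exposed to pembrolizumab could then go unrecorded and unfollowed unless it comes up in the history, the AE review or counseling.

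**Working it through.** The protocol states no figure here, so the check compares the text and then works out how long an undetected interval could be.

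**1. Is the test supplied anywhere at exit?**

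| Place | Pregnancy test at early termination |
|---|---|
| Section 6.4 list | Not named |
| Section 7 safety labs (contents of the clinical blood draw) | Not included |
| Appendix B, pregnancy-test row | 13 marks: screening, baseline and 11 clinic visits (weeks 1, 2, 3, 4, 6, 9, 12, 16, 24, 36, 48); early termination cell blank |
| Section 12.6, safety-only follow-up | Optional; content not defined |

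**2. Who is told to report at once?** The participant instruction in Section 12.3.2.4 names only those who impregnate a partner. The obstetrician advice in that section and the pregnancy trigger for unblinding in Section 5.5.1 also refer only to a partner. The site-to-sponsor reporting, the unblinding step and the regular contact in Section 12.3.2.4 apply to any pregnancy, so a participant's own pregnancy is covered once it is known.

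**3. Time since the last scheduled test, for an exit by day 120.** Inputs: visit weeks and windows from Section 6.3 (±4 days through week 6, ±7 days from week 9), with no visit missed. Test days from dosing are 0, 7, 14, 21, 28, 42, 63, 84 and 112.

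Nominal maximum = next test day − last test day. Maximum with windows = latest permitted day of the next visit − earliest permitted day of the last.

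| Exit between | Nominal maximum (days) | Maximum with windows (days) |
|---|---|---|
| Baseline and week 1 | 7 | 11 − 0 = 11 |
| Weeks 1–2, 2–3, 3–4 | 7 each | 15 each (e.g. 18 − 3) |
| Weeks 4–6 | 14 | 46 − 24 = 22 |
| Weeks 6–9 | 21 | 70 − 38 = 32 |
| Weeks 9–12 | 21 | 91 − 56 = 35 |
| Weeks 12–16 | 28 | 119 − 77 = 42 |
| Week 16 to day 120 | 120 − 112 = 8 | 120 − 105 = 15 |

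**4. Average interval.** Assume exits are uniform over days 0–120. The mean time since the last test is the sum of squared gaps divided by twice the window:

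(4×49 + 196 + 2×441 + 784 + 64) / (2×120) = 2122 / 240 = 8.8 days.

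**5. Days left in the window after exit.** If the last test and the exit are at week 6, 120 − 42 = 78 days remain. At week 12, 120 − 84 = 36 days remain. An exit test cannot cover these days. They rest on the participant telling the site.

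**The case against.** The strongest reply is that Section 6.4 models the exit visit on the follow-up visits, which include the test, and that its list is not complete: it also omits birth-control counseling, which Appendix B does mark at exit. Silence in Section 6.4 alone would therefore prove little. That is fair as far as it goes. But for counseling the table fills the gap in the prose, whereas for the pregnancy test prose and table agree on leaving it out. Staff working from the schedule would not do it. The table is imperfect in this copy (the row label is garbled, and the exit counseling mark carries a telephone footnote), but the 13 marks in the row are readable.

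Other points stand and limit the weight of the finding:

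- **Single dose.** No later dose depends on an exit test, so a positive result cannot prevent exposure. It only brings recognition and follow-up forward.
- **Rare chain of events.** Contraception or abstinence is required, and anyone leaving at a scheduled visit has just been tested. The 32 to 42 day figures need extreme visit timing at both ends.
- **Limits of one test.** It can miss a very recent conception and says nothing about the days after exit.
- **Consent form.** It is not in this copy and may tell women to report a pregnancy. The finding concerns the protocol text only.
- **Partner wording elsewhere.** The wording in Section 5.5.1 and in the obstetrician advice has little practical effect, because Section 12.3.2.4 already orders unblinding for any pregnancy.

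**Conclusion.** Both parts hold on the protocol text: no pregnancy test is listed at an early termination visit inside the 120-day window, and the immediate-notification instruction leaves out the participant who becomes pregnant herself. The claim is not that her pregnancy would go unreported once known. It is that, at exit and afterwards, the site's knowledge depends on her disclosing it.

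The likely number affected is small: women of childbearing potential among 20 participants (15 on drug under 3:1 allocation; the number of women is not stated) who leave before day 120 and attend the exit visit. At that visit the unmonitored interval is nominally at most 28 days (42 with visit windows, no visit missed), with a mean of about 9 days under the uniform-exit assumption. A rare but potentially serious fetal exposure, set against a near-costless correction, makes this a change that should be made. No endpoint, analysis or sample size figure is affected.

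**What to change.** 1. In Section 6.4 and Appendix B, add the urine or serum pregnancy test already in use, for participants of childbearing potential, at any early termination visit within 120 days of dosing. A timing footnote is enough. Footnote b already does this for the exit exam and blood draw: "This assessment will only be conducted if the early termination visit is on or before week 48".
2. In Section 12.3.2.4, instruct participants who become pregnant, as well as those who impregnate a partner, to inform the investigator immediately, including after early exit, through day 120. This covers the days an exit test cannot.
3. As tidying only, address the obstetrician advice to the participant or the partner as applicable, and name pregnancy of a participant as well as of a partner in Section 5.5.1.

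The cost is one inexpensive test at a visit that already draws blood, one footnote, and a few words in two sections.

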8.1 Potential Risks

Pembrolizumab ²⁶: The clinical safety profile of pembrolizumab is based on studies conducted exclusively in patients with a variety of cancers, the majority with melanoma and non–small cell lung cancer; many of these patients had received prior chemotherapy as well as other immunomodulatory drugs, and most patients received multiple doses of pembrolizumab, with dosing every 2 to 3 weeks. Thus, it is currently

unknown if, and with what frequency, the AEs seen in these patient populations will occur in HIV-infected patients.

The most commonly reported AEs of pembrolizumab (> 5% of patients) are fatigue, fever, pruritus, diarrhea, nausea, vomiting, decreased appetite, rash, dyspnea, constipation, asthenia, arthralgia, back pain, cough, headache, peripheral edema, anemia, myalgias, and vitiligo. Other AEs include chills, constipation, abdominal pain, dizziness, insomnia, upper respiratory tract infection, and laboratory abnormalities including increased ALT and AST, hyperglycemia, hyponatremia, hypoalbuminemia, and hypertriglyceridemia.

Pembrolizumab inhibits an immune checkpoint, and thus there is the potential for development of immune-related complications. Treatment-emergent immune-mediated diseases have been observed in cancer trials, and include pneumonitis, colitis, hepatitis, hypophysitis, thyroid disorders (hyper- and hypothyroidism, and thyroiditis), type 1 diabetes mellitus (DM), and nephritis and renal dysfunction (Table 1).²⁷ Rare potentially immune-mediated diseases include uveitis (0.5%) and other ocular disorders, myositis (0.5%), pancreatitis (0.3%), arthritis (1.5%), and Guillain-Barre syndrome (0.1%). There have been rare reports of primary adrenal insufficiency, hypoparathyroidism, myasthenia gravis, vasculitis, hemolytic anemia, autoimmune thrombocytopenia, hemophagocytic lymphohistiocytosis, systemic inflammatory response syndrome, histiocytic necrotizing lymphadenitis, sarcoidosis, gastritis, duodenitis, polymyalgia rheumatica, meningitis, myelitis, encephalitis and other neurologic disorders, pericarditis, myocarditis, some of which have been fatal, as well as severe skin reactions including Stevens-Johnson syndrome, toxic epidermal necrolysis (some cases with fatal outcome), exfoliative dermatitis, and bullous pemphigoid. Onset of immune-mediated complications typically occurred between 1 and 5 months, though onset has been reported as early as 1 day and as late as 21 months after initiation of pembrolizumab, and can occur after discontinuation of the drug.²⁷ Management (Appendix A) includes treating with corticosteroids (e.g., prednisone, 1-2 mg/kg/day followed by a taper); hypothyroidism may be treated with levothyroxine. Very rarely, immune-mediated pneumonitis has been fatal.

Of the 2799 patients treated with pembrolizumab in the Merck Reference Safety Dataset, there were 10 deaths attributed to the drug: respiratory failure (n = 1), cardio-respiratory arrest (n = 1), interstitial lung disease (n = 1), general physical health deterioration (n = 1), myocardial infarction (n = 1), pneumonia (n = 2), and pneumonitis (n = 3).²⁷

Table 1. Immune-mediated Adverse Reactions

Adverse Reaction	All Grades (%)	Grade 2 (%)	Grade 3 (%)	Grade 4 (%)	Grade 5 (%)
Hypothyroidism	8.5	6.2	0.1	0	0
Hyperthyroidism	3.4	0.8	0.1	0	0
Pneumonitis	3.4	1.3	0.9	0.3	0.1
Colitis	1.7	0.4	1.1	< 0.1	0
Hepatitis	0.7	0.1	0.4	< 0.1	0
Hypophysitis	0.6	0.2	0.3	< 0.1	0
Nephritis	0.3	0.1	0.1	< 0.1	0
Type 1 diabetes mellitus	0.2	< 0.1	0.1	0.1	0

Pembrolizumab dose = 2 mg/kg every 3 weeks or 10 mg/kg every 2 or 3 weeks.
 n = 2799.

Anti-pembrolizumab antibodies can potentially develop with treatment since pembrolizumab is a monoclonal antibody. In clinical studies, the incidence of development of anti-pembrolizumab antibodies was 2% of 1289 evaluable patients.²⁷ The clinical significance of these antibodies is uncertain. There is also the risk of allergic or anaphylactic reactions. Infusion-related reactions reported in other clinical trials include rigors, chills, wheezing, pruritus, flushing, rash, hypotension, hypoxemia, and fever, with an overall incidence of 2.5%.²⁷ In this study, all participants will be monitored during and for 2 hours after infusion so these potential reactions can be immediately cared for.

There may be other risks of pembrolizumab that are currently unknown.

Leukapheresis: The potential risks associated with leukapheresis include lightheadedness, dizziness, possible fainting, tingling around the mouth and in the fingers and toes, nausea, chills, vomiting, mild muscle cramps, loss of less than 1 pint of blood, or pain, bruising, or discomfort at the needle insertion sites. Most procedures are performed without an incident. Blood components removed during leukapheresis are generally replaced by the body within a few hours or a few days. No infections

associated with this procedure have been reported in thousands of cases performed over the last 10 years at the NIH.

Temporary or permanent nerve damage may also occur at the needle placement sites. This is very rare. There have been no cases of permanent nerve damage with apheresis reported at the NIH.

Blood draw and IV catheter: The risks of drawing blood or inserting an IV catheter for study drug/placebo infusion include pain, bruising, bleeding, and, rarely, fainting or infection.

HLA typing: HLA typing will be performed on samples collected from all enrolled participants, unless previously performed at NIH. Results from the HLA typing will become part of each participant's medical record at the NIH. Medical records containing this information are maintained in a secure place. Some HLA types have been associated with an increased risk of certain diseases like arthritis and other rheumatologic disorders, or a faster progression to AIDS. Therefore, results of genetic testing may have psychological implications for participants. Genetic counseling and advice is available from the NIH to help participants with the implications of findings, where appropriate.

8.2 Potential Benefits

Participants will likely not receive direct benefit in this study. It is possible that pembrolizumab may result in temporary improvement in anti-HIV host immunity. The information collected in this study may enhance the investigators' understanding of the use of pembrolizumab as an immunomodulatory drug for treating HIV infection.

9 Research Use of Stored Human Samples, Specimens, or Data

Intended Use: Samples, specimens, and data collected under this protocol will be used to study the potential role of pembrolizumab for treatment of HIV infection and may be used to study immune function and immune mechanisms, HIV infection and its complications, and HIV immunopathogenesis.

Storage: All of the stored study research samples are labeled by a code that only the investigators can link to the participant. Samples are stored at the NCI at Frederick Central Repository, which is a secure facility with limited access. Data will be kept in password-protected computers. Only investigators or their designees will have access to the samples and data.

Tracking: Samples will be tracked using the NCI at Frederick Central Repository. Data will be stored and maintained in the CRIMSON database.

Disposition at the Completion of the Protocol:

- In the future, other investigators (both at NIH and outside) may wish to study these samples and/or data. Before any sharing of samples, data, or clinical information, either IRB approval must be obtained or the NIH Office of Human Subjects Research Protections (OHSRP) must determine that the research is exempt from IRB oversight. OHSRP can make this determination for some research where the samples or data have no personal identifying information about the study participant and the researcher is not able to ascertain it.
- At the time of protocol termination, samples will either be destroyed, or after IRB approval, transferred to another existing protocol. Data will be archived by the study team in compliance with requirements for retention of research records; alternatively, after IRB and study sponsor approval, the data may be either destroyed or transferred to another repository.

Reporting the Loss or Destruction of Samples/Specimens/Data to the IRB:

- Any loss or unanticipated destruction of samples (for example, due to freezer malfunction) or data (for example, misplacing a printout of data with identifiers) that meets the definition of protocol deviation, unanticipated problem (UP), and/or compromises the scientific integrity of the data collected for the study will be reported to the NIAID IRB.
- Additionally, participants may decide at any point not to have their samples stored. In this case, the PI will destroy all known remaining samples and report what was done to both the participant and to the IRB. This decision will not affect the individual's participation in this protocol or any other protocols at NIH.

10 Data Sharing Plan

Human data generated in this study will be shared for future research as follows:

- Identified data in the Biomedical Translational Research Information System (BTRIS; automatic for activities in the CC).
- De-identified or identified data with approved outside collaborators under appropriate agreements.
- Through publication and/or public presentations.
- Data sharing may be complicated or limited in certain cases by contractual obligations or agreements with outside collaborators, such as a cooperative

research and development agreements, clinical trial agreements, other restraints, etc.

Data will be shared at the time of publication.

11 Remuneration Plan for Participants

Eligible participants will be compensated for travel according to the NIAID/NIH travel policy. Participants will receive financial compensation for time and inconvenience according to the NIH CC volunteer guidelines: screening (\$50), 2-pass leukapheresis (\$200 for a procedure; \$50 for unsuccessful apheresis attempts), research blood draw and clinic visits (\$75), pembrolizumab/placebo infusion (\$150). If a participant does not qualify or declines leukapheresis, then an additional 80 mL of research blood will be drawn, and the participant may be compensated an additional \$25 for inconvenience. If a participant completes all visits in the follow up phase of the study, there is a \$200 completion bonus. Actual compensation is based on the number and type of study visits participants complete. Therefore, the maximum remuneration for a participant is \$1900.

12 Assessment of Safety

AEs and other reportable events are defined in Policy 801: Reporting Research Events

Adverse Reaction: An AE that is caused by an investigational agent (drug or biologic).

Suspected Adverse Reaction (SAR): An AE for which there is a reasonable possibility that the investigational agent caused the AE. "Reasonable possibility" means that there is evidence to suggest a causal relationship between the drug and the AE. An SAR implies a lesser degree of certainty about causality than AR, which implies a high degree of certainty.

